9.7.3.3 ANALYSIS OF EXPLORATORY ENDPOINTS RELATED TO PRO

For analyses of PRO using SBS-IF-CIC-QOL, the change in scores from baseline to scheduled visit will be summarized by descriptive statistics. *p*-values and Hodges-Lehmann median estimator along with 95% CI will be produced for Week 24 and Week 52 as defined in the introduction of Section 9.7.

For analyses of PRO using SBS-IF-TI-QOL, PS impact subscale and GLP-2 impact subscale scores will be summarized by scheduled visit using descriptive statistics along with the descriptive statistics of two item values in Part 2 regarding GLP-2 impact.

For SBS-IF-CIC-QOL, it is assumed that the score will be calculated by taking the mean of the 14 items. For SBS-IF-TI-QOL, it is assumed that two subscale scores will be calculated, PS impact, and GLP-2 impact. The PS impact subscale will be calculated for the subjects with CIC by taking the mean of items 1 to 10 in Part 1. The GLP-2 impact subscale will be calculated by taking the mean of items 1 and 2 in Part 2.

In case at least one item is missing (i.e. not reported), the mean will not be calculated with the

following exceptions: In case of SBS-IF-TI-QOL item(s) 1 or 9 being reported as N/A, the PS impact subscale will be calculated by taking mean of the relevant item responses. In case of SBS-IF-TI-QOL item 2 response being not reported or N/A in Part 2, the GLP-2 impact subscale will be calculated only based on item 1 response since item 2 may not be relevant for subjects who do not prepare GLP-2 injection themselves

[REDACTED]

9.7.4 SENSITIVITY ANALYSIS TO THE EFFICACY ANALYSES

The analyses of the following endpoints related to nutritional status and nutritional absorption will be repeated for sensitivity analyses using a subgroup of subjects in the FAS excluding subjects missing more than 20% of the planned injections prior to the respective visit. Hence, the number of injections leading to exclusion will be 1 at Week 4, 5 at Week 24, and 10 at Week 48. In other words, the subgroup for Week 4 analysis will be composed of subjects in the FAS with at least 4 injections prior to the visit date of Week 4 assuming 4 planned injections prior to Week 4. Similarly, the subgroup for Week 24 analysis will be composed of subjects in the FAS with at least 20 injections prior to the visit date of Week 24, whereas the subgroup for Week 48 analysis will be composed of subjects in the FAS with at least 39 injections prior to the visit date of Week 48.

- Change in absorption of energy and wet weight over the MB period from baseline to Week 4 and Week 48
- Relative change in absorption of energy and wet weight over the MB period from baseline to Week 48
- Change in absorption of macronutrients (fat, carbohydrate, and protein) over the MB period from baseline to Week 4 and to Week 48
- Change in urine output and urinary electrolytes (calcium, magnesium, sodium, potassium, urea, and creatinine) over the MB periods from baseline to Week 4 and Week 48
- Changes from baseline in lean body mass, bone mineral content and fat mass by DEXA scan from baseline to Week 4, Week 24, and Week 48
- Change in body weight from baseline to Week 4, Week 24 and Week 48
- Change in dietary intake of wet weight (oral solid food, oral fluid), energy, macronutrients (fat, carbohydrate, nitrogen, and protein), and electrolytes (sodium, potassium, calcium and magnesium) from baseline to Weeks 4 and 48
- Change in fecal excretion of wet weight (feces), energy, macronutrients (fat, carbohydrate, nitrogen, and protein), and electrolytes (sodium, potassium, calcium and magnesium) from baseline at Weeks 4 and 48

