- If at any visit the subject shows signs of significant fluid overload, leading to clinical decompensation, the Investigator should consider PS reduction. An AESI of fluid overload must be reported. In all cases this reduction must be discussed with the medical monitor either before or after reduction
- Patient reported outcomes collected as follows (with the following preferred order):
 - At Baseline: SBS-IF-CIC-QOL, PGI-S, PGI-PSI, PGI-SPS, PGIC (1.0), PGIC (2.0)
 - At Weeks 4, 12, and 36: SBS-IF-CIC-QOL, SBS-IF-T1-QOL, PGI-S, PGI-PSI, PGI-SPS, PGIC (1.0), PGIC (2.0)
 - At Weeks 24, 52, and EOT visit: SBS-IF-CIC-QOL, SBS-IF-T1-QOL, PGI-S, PGI-PSI, PGI-TS, PGI-SPS, PGIC (1.0), PGIC (2.0)
 Only subjects that completed version 1.0 of the PGIC and PGI-S at baseline continue to complete these during the trial
- See [Table 2](#) Schedule of Assessments for metabolic balance periods
- The visit window of ± 1 week or ± 2 weeks allows a shift in the visit 7 or 14 days (± 1 day) from Baseline calculated visits. Visits should be done at the same day of the week with a window of ± 1 day. Investigational medicinal product administrations during a week with a site visit must be done at the site
- If biopsies are required a colonoscopy will NOT be performed unless a full view of the colon to check for polyps was not possible during the colonoscopy
- Optional assessments
- When deemed anatomically feasible by the Investigator, colonoscopy or colonography should be performed within ± 3 weeks of end of treatment
- ECG, physical exam and vital signs should be recorded prior to blood sampling and prior to IMP administration
- Subjects to be asked to measure their body weight weekly and record results in the e-diary. Body height will be measured once at screening only
- Adverse events and AESIs should be recorded starting after obtaining informed consent (see [Section 6.1](#))
- Telephone contact will be made every 7 days (± 1 day) during screening. During each contact, AEs will be collected and changes in concomitant medications recorded
- At all contacts the subject will be asked to recollect the frequency and severity of nausea, vomiting, and abdominal pain in the preceding 7 days. This information will also be collected at Visit 3, pre-dose. At Week 0, Day 1 (± 1 day), the subject will be contacted to assess for fluid overload and frequency of stools

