4.2 TRIAL TREATMENT

A single 2.5 mg dose (for subjects with body weight less than 50 kg at most recent trial visit) or 5 mg dose (for subjects with body weight 50 kg or more at most recent trial visit) of apraglutide will be administered by SC injection once weekly during a treatment period of 52 weeks.

IMP should be administered on the same day of the week based on the first administration at Week 0 (Visit 3), with a window of \pm 24 hours, i.e., the administration could be done up to

24hours earlier or later than per schedule. On days when the subject will be at the site, the IMP must be administered at the site. Change of dosing is only allowed at each clinic visit. Between visits, IMP can be either self-administered at home or by a family member/caregiver, or administered at the clinic.

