9.2 DEFINITION OF BASELINE, TRIAL VISITS, AND VISIT WINDOWS

The baseline is the last available assessment/observation prior to first trial treatment (i.e. first administration of apraglutide). For assessments done on the same day as the first trial treatment, the time of assessment should be used to recognize whether or not the assessment was done prior to the first trial treatment. Otherwise, when the time of assessment is not available, last available assessments on or prior to the date of first trial treatment will be

considered as baseline since assessments are to be performed prior to dosing on the day of the first IMP administration according to the schedule of assessments in the protocol.

For evaluation of MB parameters, all relevant data measured over the MB period at the scheduled visit will be considered as the analysis timepoint. This applies to baseline, Week 4, and Week 48. The detailed derivation of baseline MB period data can be found in Section 9.7. Except for EOT visit data for efficacy analyses, by-visit efficacy data will be analyzed based on eCRF visits.

For all efficacy analyses, the EOT visit data will be mapped to a visit as defined below and will be only used to replace any missing by-visit efficacy data:

Table 9.2.1: Data Mapping Scheme

Visit	Analysis timepoint	Target day*	
4	Week 2	Day 15	
5	Week 4	Day 29	
6	Week 8	Day 57	
7	Week 12	Day 85	
8	Week 16	Day 113	
9	Week 20	Day 141	
10	Week 24	Day 169	
11	Week 28	Day 197	
12	Week 32	Day 225	
13	Week 36	Day 253	
14	Week 40	Day 281	
15	Week 44	Day 309	
16	Week 48	Day 337	
17	Week 52	Day 365	

*based on the relative days from the first trial treatment where the relative days from the first trial treatment = date of assessment or event – date of first trial treatment + 1, when both dates are known for assessments or events started on or after the day of the first trial treatment. (e.g., Relative Study Day 1 = the first study dosing day)

For safety data analysis, by-visit data will be analyzed based on the assigned analysis visit based on the data mapping scheme above. If more than one assessment falls into allowed time window the closest to the target date will be used. If two values are equidistant from the planned visit/assessment date, the first value will be used.

The citrulline and apraglutide plasma concentration data will be analyzed by scheduled visit based on eCRF visit (including EOT where applicable).

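### The missed-injection sensitivity set in SAP 9.7.4 uses fixed counts that agree with its own 20% rule, and with each other, only when the visit falls on schedule

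*SAP*

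**What the plan says.** SAP 9.7.4 defines the sensitivity subgroup by a proportion, "excluding subjects missing more than 20% of the planned injections prior to the respective visit". It then puts that rule into numbers twice.

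- **Missed counts:** "the number of injections leading to exclusion will be 1 at Week 4, 5 at Week 24, and 10 at Week 48".
- **Received counts:** "at least 4 injections prior to the visit date of Week 4 assuming 4 planned injections prior to Week 4"; then "subjects in the FAS with at least 20 injections prior to the visit date of Week 24"; then "at least 39 injections prior to the visit date of Week 48". A planned number is written out only for Week 4.

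Three other provisions bear on this:

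- **Dosing.** The drug is "administered by SC injection once weekly during a treatment period of 52 weeks" (SAP 4.2), with the first dose at Week 0.
- **Visit timing.** The visit-window footnote to Protocol Table 1 "allows a shift in the visit 7 or 14 days". The Week 24 window is ±2 weeks in the schedules of both documents. The Week 48 window is ±1 week in SAP Appendix 1 and ±2 weeks in the protocol table as extracted, whose columns are visibly disturbed. Protocol 2.2.2 describes visits after Week 4 as every 4 weeks ±1 week. Week 4 carries no window.
- **Visit labels.** Apart from end-of-trial data, "by-visit efficacy data will be analyzed based on eCRF visits" (SAP 9.2), so a shifted visit keeps its nominal label.

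SAP section 10 changes the protocol's counts (6 at Week 24, 11 at Week 52) to 5 at Week 24 and 10 at Week 48 so that they follow the 20% rule. It does not address actual visit timing.

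**The concern.** The rule is a proportion, and its denominator is the number of doses planned before the visit. With weekly dosing, that number changes by one for each week the visit moves. The counts 20 and 39 received, and 5 and 10 missed, are each tied to one denominator, 24 or 48, yet injections are counted up to the actual visit date. An early visit leaves less time to reach the fixed received count; a late visit leaves more.

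Two things are at stake. The set may drop a subject who meets the 20% rule, or keep one who does not. And the two count rules in the same paragraph can disagree, so two programmers following the SAP could build different sets.

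**Working it through.** **Inputs.** The rule is missed/planned > 20%; the missed counts are 1/5/10 and the received counts 4/20/39 (SAP 9.7.4). Dosing is weekly from Week 0 (SAP 4.2). Windows are as listed above. A visit held at week p has p doses planned before the visit-week dose.

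**Formula.** With r doses received, percent missed = (p − r)/p, and a subject is kept if this is at most 20%. The minimum r is therefore 0.8p rounded up.

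**The plan's own figures.** 20% of 4, 24 and 48 is 0.8, 4.8 and 9.6. Exclusion therefore starts at 1, 5 and 10 missed, and inclusion at 4, 20 and 39 received. Both sets of SAP counts are reproduced.

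**Shifted visits.** The last two columns show where each count rule departs from the 20% rule.

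| Visit held at week (p planned) | Minimum received under 20% rule | SAP received count | Error from received count | Error from missed count (5 or 10) |
|---|---|---|---|---|
| 22 | 18 | 20 | 18/22 (18.2% missed) and 19/22 (13.6%) excluded | none |
| 23 | 19 | 20 | 19/23 (17.4%) excluded | none |
| 24 | 20 | 20 | none | none |
| 25 | 20 | 20 | none | 20/25 (20.0%) excluded |
| 26 | 21 | 20 | 20/26 (23.1%) kept | 21/26 (19.2%) excluded |
| 47 | 38 | 39 | 38/47 (19.1%) excluded | none |
| 48 | 39 | 39 | none | none |
| 49 | 40 | 39 | 39/49 (20.4%) kept | none |

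20/25 counts as an error because exactly 20% is not more than 20%.

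**Only if the Week 48 window is ±2 weeks.** At 46 planned, the received count excludes 37/46 (19.6%) and 38/46 (17.4%). At 50 planned, it keeps 39/50 (22.0%), and the missed count excludes 40/50 (20.0%).

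**Share of doses the received count lets a subject miss.** This is (p − 20)/p at the Week 24 timepoint: 2/22 = 9.1% at Week 22, rising to 6/26 = 23.1% at Week 26. At the Week 48 timepoint it is (p − 39)/p: 8/47 = 17.0% to 10/49 = 20.4% under ±1 week.

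**Disagreement between the two count rules.** 18/22 has 4 missed, so the missed count keeps it and the received count drops it. 21/26 has 5 missed, so the missed count drops it and the received count keeps it.

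**Weight of one subject.** The SAP Introduction reports 7 + 2 = 9 enrolled; 1/9 = 11.1% if all are in the full analysis set.

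**The case against.** The strongest reply is that the missed-count sentence already classifies correctly every case the received counts get wrong: 18/22, 19/22, 19/23 and 38/47 miss 4, 3, 4 and 9 and stay in; 20/26 and 39/49 miss 6 and 10 and go out. That stands. It does not close the point, because the received counts are the explicit definition of the set, and the missed counts have errors of their own at 25 and 26 planned doses.

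A second reply is that a nominal denominator is a stated assumption at Week 4 and carries over by analogy. That is a fair reading of the drafting. But injections would still be counted to a shifted date, so numerator and denominator would cover different periods.

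Several stronger readings are tempting, and the documents do not support them:

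- **That the SAP's counts are miscalculated.** They are exact on schedule.
- **That fully adherent subjects are dropped.** A subject with no missed dose always passes: 22 is at least 20, and 47 (or 46) is at least 39.
- **That every off-schedule visit misclassifies.** A Week 25 visit gives no error under the received counts, and elsewhere only one or two exact dose totals are affected.
- **That 46 to 50 doses may be planned by Week 48.** This needs the ±2 reading of the protocol table; the SAP schedule gives ±1.
- **That the absorption results are exposed at Week 24.** In the SAP 9.7.4 list, Week 24 applies only to the DEXA and body weight analyses, both exploratory.

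There is also some mitigation. SAP 9.8.1 summarises overall compliance at 80% and lists all dosing data, so a borderline subject would be visible in a trial this small.

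**Conclusion.** The point holds as a minor one. SAP 9.7.4 states a proportional rule and implements it with two fixed-count rules that match it, and each other, only with exactly 24 and 48 doses planned by the visit. Under the narrowest reading of the windows (±1 week), the received counts misclassify 19/23, 38/47 and 39/49, and the missed counts misclassify 20/25. The ±2 window at Week 24 adds 18/22, 19/22 and 20/26 to the first list and 21/26 to the second.

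This rests on planned doses following actual weeks elapsed and on visits moving by whole weeks. Week 4 is unaffected. Nothing in the documents shows that any subject lies near the threshold, so the effect of one subject is a possibility and not an observed result. The main efficacy analyses do not depend on this set. The Appendix 4 note to file overrides the SAP and is not reproduced; it may already deal with the matter.

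**What to change.** Check the note to file first. If it is silent, replace both fixed-count sentences in SAP 9.7.4 with one per-subject definition:

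percent missed = (weekly doses scheduled before the visit-week dose, at the actual visit, − doses received before the visit-week dose) / weekly doses scheduled before the visit-week dose; exclude if above 20%.

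Keep 4, 20 and 39 only as the on-schedule illustration.

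The visit-week dose must be left out of both numerator and denominator. It is given at site, and the footnote allows the visit day to move by ±1 day. If planned doses were instead counted to the day before the visit, a Week 48 visit on Day 338 rather than Day 337 would add a planned dose not yet given. A subject with 39 doses would then show 10/49 = 20.4% missed and be excluded, although 9/48 = 18.75% of the doses due had been missed.

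The cost is one sentence and a small change to the program. Dosing dates are already collected, and SAP 9.8.1 already derives planned weeks per subject from dates. The definition works under either Week 48 window.

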9.8 SAFETY ENDPOINTS AND ANALYSIS

The primary endpoints of this study are the safety endpoints as specified in Section 7.1.

9.8.1 EXPOSURE TO TRIAL TREATMENT

The extent of trial treatment exposure will be summarized descriptively by the following:

- Trial treatment duration (weeks). To be derived as follows: $(\text{date of last trial treatment} - \text{date of first trial treatment} + 1)/7$, when both dates are known.
- Cumulative treatment exposure (mg). To be based on the total amount of trial medication taken by a subject as determined using diary and information provided by sites.
- Compliance (%). To be calculated as follows: $[\text{total amount of drug taken by a subject (based on diary and site information)} / ((\text{number of weeks when a subject was assigned a dose of 2.5 mg}) * 2.5 + (\text{number of weeks when a subject was assigned a dose of 5 mg}) * 5)] * 100$, where the number of weeks for the assigned dose will be calculated as follows: $(\text{stop date of the respective dose} - \text{start date of the respective dose} + 1)/7$, rounded up to the next higher integer to represent the planned number of weeks for the assigned dose.

The compliance will be also summarized categorically by $\geq 80\%$ and $< 80\%$.

The frequency (%) of dose reductions and trial treatment discontinuation will be summarized as a part of safety analyses (See Section [9.8.2](#))

All IMP administration data will be listed.

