4. TRIAL INTERVENTION/MEDICATION

4.1 Description of Investigational Medicinal Product (IMP)

All subjects will receive, based on their body weight, either 2.5 mg or 5 mg apraglutide once weekly, for 52 weeks. The IMP will be administered SC.

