4.2 Administration of Experimental Intervention

4.2.1 Experimental Intervention

A single 2.5 mg dose (for subjects with body weight less than 50 kg at most recent trial visit) or 5 mg dose (for subjects with body weight 50 kg or more at most recent trial visit) of apraglutide will be administered by SC injection once weekly during a treatment period of 52 weeks. Change of dosing is only allowed at each clinic visit, after obtaining the subject's current weight ([Table 1](#) and [Table 2](#)).

The IMP should be administered on the same day of the week based on the first administration at Visit 3, with a window of ± 24 hours, i.e., the administration could be done up to 24 hours earlier or later than per schedule. On days when the subject will be at site, the IMP must be administered at site. Detailed instructions will be provided in the Pharmacy Manual.

Between clinical trial visits, IMP can be administered at home. The subject or the caregiver will receive training in SC administration of IMP using a training kit containing placebo vials. The decision to select IMP administration at site or at home will be determined based on subject capability to self-administer at home, subject preference and clinical considerations. The subject will record IMP administration information in the e-diary. Detailed instructions will be provided in the Trial Medication Manual for Subjects.

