Efficacy																		
Prescribed PS volume, composition, days per week	X	X	X	X	X	X	X	X	X	X	X	X	X	X	X	X	X	X ¹⁵
Define and confirm drinking menu ¹⁶	X	X																
Patient Reported Outcome (PRO) questionnaires ²		X			X		X			X			X				X	X
Change in Eating/Appetite		X		X	X	X	X	X	X	X	X	X	X	X	X	X	X	X
Urine sample for sodium analysis (from sample taken during 48-hour urine collection, balance period) ¹⁶		X ¹⁷		X	X ¹⁷	X	X	X	X	X	X	X	X	X	X	X ¹⁷	X	
DEXA Scan		X			X					X						X		
Gastroduodenoscopy	X									X ⁶						X ²³		
Trial Medication and																		

	Screening	Baseline	Treatment Period														End of trial	
Visit No. ¹	1	2 ³	3	4	5 ³	6	7	8	9	10 ²⁶	11	12	13	14	15	16 ³	17	18
Week (weeks unless indicated)	-4 to -2 (Day -28 to -14)	-1 (Day-7 to -3)	0 (Day 0)	2 (+1)	4	8 ⁴ (±1)	12 (±2)	16 (±2)	20 (±2)	24 (±2)	28 (±2)	32 (±2)	36 (±2)	40 (±2)	44 (±2)	48 (±1)	52 (±2)	4 weeks after last dose ±1 week
Diary																		
Hand out subject e-diary	X																	
Subjects complete diary prior to the visit		X		X	X	X	X	X	X	X	X	X	X	X	X	X	X	
Review all subject diary information since last visit		X		X	X	X	X	X	X	X	X	X	X	X	X	X	X	
SC injection of IMP at site			X	X	X	X	X	X	X	X	X	X	X	X	X	X		
Instruct subject in IMP handling at home and assess self-administration capability ¹⁸			X															
Dispense IMP			X	X	X	X	X	X	X	X	X	X	X	X	X	X		
Return home administered IMP vials to site				X	X	X	X	X	X	X	X	X	X	X	X	X	X	
																		
																		

	Screening	Baseline	Treatment Period														End of trial	
Visit No. ¹	1	2 ³	3	4	5 ³	6	7	8	9	10 ²⁶	11	12	13	14	15	16 ³	17	18
Week (weeks unless indicated)	-4 to -2 (Day -28 to -14)	-1 (Day-7 to -3)	0 (Day 0)	2 (+1)	4	8 ⁴ (±1)	12 (±2)	16 (±2)	20 (±2)	24 (±2)	28 (±2)	32 (±2)	36 (±2)	40 (±2)	44 (±2)	48 (±1)	52 (±2)	4 weeks after last dose ±1 week
[REDACTED]		■			■					■						■		
[REDACTED]		■			■					■						■		
[REDACTED]	■									■						■		
[REDACTED]	■									■						■		
[REDACTED]		■			■					■						■		
[REDACTED]		■			■					■						■		
[REDACTED]		■			■					■						■		
[REDACTED]		■			■					■						■		

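### SAP 9.8.1 computes weekly-dosing exposure with a day-count formula: duration reads 0.86 week low for every subject, and the rounded-up compliance denominator can be one dose out within the allowed dosing window

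*SAP*

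**What the plan says.** SAP 9.8.1 lists three exposure summaries.

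- **Duration.** "Trial treatment duration (weeks). To be derived as follows": the date of the last trial treatment minus the date of the first, plus 1, divided by 7.
- **Cumulative exposure.** Total mg taken.
- **Compliance.** Total mg taken, divided by the weeks assigned to 2.5 mg times 2.5 plus the weeks assigned to 5 mg times 5, as a percentage. The weeks at each dose are (stop date − start date + 1)/7, "rounded up to the next higher integer to represent the planned number of weeks for the assigned dose". Compliance is also split at 80%.

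The SAP does not define the stop date of a dose. It could be the last injection at that dose or the end of the period to which the dose was assigned.

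On dosing, the protocol (4.1) has "apraglutide once weekly, for 52 weeks", and SAP 4.2 says the drug "will be administered by SC injection once weekly during a treatment period of 52 weeks". Protocol 4.2.1 adds that "the administration could be done up to 24 hours earlier or later than per schedule". The dose level may change at a clinic visit according to body weight (Protocol 4.2.1) or be reduced for safety (Protocol 6.6.1), so a subject can have more than one assigned-dose period.

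**The concern.** Last minus first plus one is the usual duration formula for a drug taken daily, where the final dose covers one day. Here the final dose covers a week. Under the SAP formula, a subject who takes all 52 doses on schedule cannot reach 52 weeks. The shortfall is minor for completers and large in relative terms for anyone who stops early.

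The compliance denominator is meant to equal the number of planned doses. A quotient of dates that is then rounded up is sensitive to a shift of one day, and the protocol permits such shifts. At stake is whether the reported compliance, and its split at 80%, reflects doses missed or only the weekday of an injection.

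**Working it through.** **1. Planned doses.** The SAP states no numeric duration or compliance result, but its dose counts can be reproduced. With one dose a week from Week 0, there are w planned doses before Week w. More than 20% missed means at least floor(0.2w) + 1 missed, which leaves a minimum of w − floor(0.2w) injections to stay in.

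- Week 4: 1 missed excludes, minimum 4
- Week 24: 5 missed excludes, minimum 20
- Week 48: 10 missed excludes, minimum 39

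These match SAP 9.7.4, including "assuming 4 planned injections prior to Week 4" and "at least 39 injections prior to the visit date of Week 48". For w = 52 the rule gives 11, as in Protocol 7.4. In SAP Appendix 1 the row "SC injection of IMP at site" is marked at Visits 3 to 16 and blank at Visit 17 (Week 52). A full course is therefore 52 doses at Weeks 0 to 51, with the last one 51 × 7 = 357 days after the first.

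**2. Duration, d doses on schedule.** SAP: (7(d − 1) + 1)/7. With +7 in place of +1: d.

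| Doses | SAP formula (weeks) | With +7 (weeks) | Shortfall |
|---|---|---|---|
| 52 | 358/7 = 51.14 | 52 | 1.6% |
| 8 | 50/7 = 7.14 | 8 | 10.7% |
| 4 | 22/7 = 3.14 | 4 | 21.4% |
| 1 | 1/7 = 0.14 | 1 | 85.7% |

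The absolute shortfall is 6/7 = 0.86 week in every row.

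**3. Compliance denominator, 52 planned doses, ordinary rounding up.**

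| Meaning of stop date | One day early | On time | One day late |
|---|---|---|---|
| Last injection | 357/7 = 51.00 → 51 | 358/7 = 51.14 → 52 | 359/7 = 51.29 → 52 |
| End of assigned period | 363/7 = 51.86 → 52 | 364/7 = 52.00 → 52 | 365/7 = 52.14 → 53 |

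Each meaning gives a wrong count in one of the three cases. Day 365 is also the SAP's own target day for Week 52 (Table 9.2.1), so a stop date entered as that visit gives 53 even when nothing is late.

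**4. Effect on compliance, one dose level throughout.**

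- Last-injection meaning, last dose a day early: 52 taken reads 52/51 = 102.0%. With 41 taken, the true value is 41/52 = 78.8% and the reported value 41/51 = 80.4%, so the subject moves above the 80% cut.
- Period-end meaning, end a day late: 42 taken is 42/52 = 80.8% but reads 42/53 = 79.2%, so the subject moves below it.

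**5. Effect after a dose change.** Take 24 weeks at 2.5 mg then 28 at 5 mg, all doses taken, with both periods ending on a day-early injection. The denominator is 23 × 2.5 + 27 × 5 = 192.5 mg instead of 24 × 2.5 + 28 × 5 = 200 mg, and compliance reads 200/192.5 = 103.9%.

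**The case against.** The strongest case on the other side has five parts.

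- **Duration is a stated convention.** The formula is explicit and the difference is a known constant. Cumulative mg is summarized and every administration is listed, so with nine subjects enrolled (two in France, seven in Belgium; SAP 2) actual dosing stays visible. That limits the harm, but the line is labelled treatment duration, and 0.14 week for a subject given one weekly dose misdescribes it.
- **The compliance error depends on the reading.** This stands in part. If rounding always moves to a strictly larger integer, 51.00 becomes 52 and the last-injection meaning is right in all three cases. The same rule then turns an on-time 364/7 = 52.00 into 53 under the period-end meaning. The SAP fixes neither the stop date nor the rounding.
- **Exposure drives no inference.** A reader might take exposure to be the denominator for the primary safety endpoint. It is not. SAP 9.8.2 reports percentages of subjects with events and numbers of events, with no person-time rate, and its on-treatment window runs from the last dose date plus 28 days. The 9.7.4 subgroups use injection counts.
- **Short-segment figures overstate the problem.** A four-dose course with a day-early last dose reads 4/3 = 133%, and an eight-dose course 8/7 = 114%. A reader might apply these to short segments after a dose switch. Compliance is one value per subject, so they hold only when that is the whole course. With 48 doses at 5 mg and a four-dose 2.5 mg segment that loses one, the result is 250/247.5 = 101.0%. Nor do the duration line and the rounded-up weeks contradict each other as reported results, because the latter is only an intermediate term.
- **The Note to File may change this.** It supersedes the SAP (SAP 2), and SAP 8, which mentions the exposure and compliance tables, points to it. Its text is not reproduced. SAP 9.8.1 does not point to it and SAP 10 lists no such correction, so the point rests on the text available.

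**Conclusion.** The point holds as a minor correction to descriptive exposure summaries. The duration part rests only on once-weekly dosing: every subject reads 0.86 week low, which is 1.6% of a full course and far more in relative terms for early stoppers. The compliance part is conditional. Under ordinary rounding up, each meaning of the stop date can put the planned count one dose out within a one-day shift, by about 2% over a full course. That matters only for a subject near the 80% cut. The documents do not show that any subject will be misclassified, and no planned adverse event summary, efficacy result or sensitivity subgroup changes.

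**What to change.** - **Duration:** (date of last dose − date of first dose + 7)/7. A full course then reads 52.0 weeks, or 51.86 or 52.14 if the last dose is a day early or late, and one dose reads 1.0.
- **Compliance denominator:** replace the rounded-up quotient by the number of scheduled weekly doses in each assigned-dose period, up to the end of that period or treatment discontinuation, times the assigned mg. This is unaffected by a one-day shift, and doses missed at the end of a period still count.

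A denominator built from the first to the last actual injection would be stable to the window but would hide such doses: six of eight assigned doses taken, with the last two missed, would read 6/6 = 100% instead of 6/8 = 75%.

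The cost is two edits in the SAP and the matching program changes. No new data are needed.
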